2.4 Screening

Subjects will be asked questions about their medical history, have their weight recorded, may have a limited physical exam, and their inclusion/exclusion criteria will be verified. Discontinuation of any concomitant medications will be discussed, and pretreatment instructions and post treatment instruction will be reviewed with the subject.

Procedure for the Limited Physical Exam:

If the investigator determines that a limited exam is necessary, the exam will be similar to a basic annual physical exam performed by a primary care doctor to determine general overall health. The limited medical exam may include all or any of the following; vital signs such as blood pressure, heart rate, respiratory rate and body temperature, general appearance, listening to the heart, lungs and abdomen with a stethoscope, head and neck exam, in addition to examining the throat, tonsils, teeth, ears, eyes and nose as well as a neurological exam such as testing muscle strength, reflexes, balance, sensory changes of the extremities and mental state.

The following pre-treatment instructions will be reviewed:

- Shave any dense hair on the area to be treated.
- Do not wear constrictive clothing. Treatment area must be accessible. The back for the neutral pad will also need to be accessed.
- The treatment area must be free of any open lesions or infections.

- For an optimum treatment, keep hydrated by drinking water (at least 8 cups daily) or hydrating fluids, such as Gatorade, and avoid drinking alcohol for 24 hours in advance.

The following post treatment instructions will be reviewed:

- If the skin is slightly pink or red in areas following the treatment, avoid hot water when washing or showering until any erythema (redness) has subsided.
- Soothing creams or moisturizers, such as Aveeno, may be used.
- Gently massage the treated area daily for 5 minutes for the duration of your involvement in the study.
- Use a sun block with UVA and UVB protection with SPF of 30 or greater for 2 – 3 weeks after each treatment to prevent sun damage.
- Maintain the same weight and exercise routine throughout the study.

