1.1 Objectives**1. Primary Objectives:**

- Photographic evaluation with correct identification of pre-treatment images when compared to the 12 week follow up images performed by three independent reviewers.

2. Secondary Objectives:

- Caliper measurements to show statistically significant improvement on treatment area versus control.
- Subject satisfaction rates at 12 week follow up.
- Safety assessment through the collection of Adverse Events.

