2.0 PROTOCOL**2.1 Protocol Methodology and Analysis****Methodology:**

Subjects are to be enrolled in this clinical study if they are 18 – 55 years old. A maximum of 68 subjects will be enrolled at up to 6 study centers. Subject will attend a screening/pretreatment visit which may be performed on the same day as the treatment visit. Subjects will receive up to 5 treatments with the TempSure® Firm on one flank. The other flank will be left untreated to serve a control. Subject will be required to return for follow-up visits at 6 weeks and at 12 weeks after the subject's final treatment. All subjects will receive a phone call 1 week (1-10 days) post each treatment. An unscheduled visit or phone call may be performed at any time during the study at the subject's request or as deemed necessary by the site Investigator.

Analysis:

Upcoming generations are proving to have an interest in non-ablative aesthetic treatments and will drive demand for innovated products, procedures, and practice design.ⁱ Due to this shift in patient base, practices need to evolve to adapt to the newer generational ideologies. There have been rapid advances in RF technology over the past few years and the nonsurgical treatment using this energy source offers great promise to our aging population.ⁱⁱ Radiofrequency technology for lipolysis needs to be further investigated to optimize treatment parameters for safe and effective non-ablative aesthetic treatments.

Relevance:

Non-invasive fat reduction is a commonly sought out procedure and continues to increase in demand (+3% from 2018 to 2019)³ perhaps due to the fact that, according to the CDC, the prevalence of obesity in the U.S. was 42.4% in 2017-2018⁴. Currently, the treatments available for non-invasive lipolysis include, but not limited to, radiofrequency, cryolipolysis, laser lipolysis, HIFEM, and ultrasound. The limitations of current products on the market include different side effect profiles and modes of administration.

Testability:

The CoolSculpting device has been cleared for used for cold-assisted lipolysis(breakdown of fat) of bra fat, back fat, banana roll, submental area, thigh, abdomen, and flank, or "love handles" in individuals with a Body Mass Index

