2.2 Protocol Study Design

This is a prospective, open-labeled, randomized, multi-center clinical study to collect efficacy data on the TempSure® Firm.

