2.15 Statistical Analysis

2.15.1 Hypothesis

For this study to be considered a success, the following criteria must be met:

1. Correct identification of pre-treatment images when compared to post treatment (12 week) images will be $\geq 80\%$.
2. Caliper measurements show statistically significant improvement on treatment area versus control.
3. The subject satisfaction rates at 12-week follow up visit will be $\geq 80\%$.
4. The side effect profile is acceptable to the Physician as it relates to this type of treatment.

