2.15.2 Sample Size Rationale

The primary outcome will be the change in the subjective assessment of the reduction in fat as assessed by blinded evaluation of photographs taken before and after treatments. The primary endpoint will be defined as the 12-week follow up post final treatment with an objective of 80% correct evaluation. The sample size was determined based on a two-sample t-test with a two-sided significance level of 0.05 and power of 95%. A hypothetical control group would assumedly result in correct identification of follow up pictures 50% of the time, with a standard deviation of 50% resulting from an equal amount of correct and incorrect answers. Our objective of 80% correct average evaluation of post treatment photos with a conservative 20% expected standard deviation. Based on these assumptions it was determined that a total of at least 43 patients would be required for the study to have a successful primary outcome.

One of the secondary outcomes will be the change in fat layer thickness as assessed by caliper measurements before and after treatments. Previous studies have shown a change in caliper measurements of 7.0mm in a treated flank, and 0.7mm change in the control. The maximum standard deviation seen for any measurements (treated or control, baseline or follow up) was 5.8 which is used as an assumed standard deviation for sample size calculations.^v Assuming 0.05 significance level and adjusting for a power of 95%, it was determined that 14 subjects would be needed to have a successful secondary outcome measure.

Another secondary outcome is the subject satisfaction rate. The sample size is calculated similarly to the primary outcome and yields the same results.

Based on these assumptions it was determined that a total of 43 patients would be required for the study, which was the maximum calculated among all the study outcome measures. To allow for minor departures in these assumptions and to account of potential subject dropout it was decided to enroll 68 subjects.

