2.15.5 Analysis of Efficacy Variables

The primary efficacy variable is blinded evaluation of photographs from baseline to Visit 8 (12-week follow up) with respect to fat reduction. Baseline is defined as the last assessment prior to the first treatment. Photos will be graded and the total and percentage of photos correctly identified will be compiled and analyzed. Correct identification percentages will be calculated for each individual reviewer as well as a summary for all three reviewers. Clinical success of grading will be declared if 80% independent reviewers achieve 80% correct identification of the photos.

The secondary efficacy variables are caliper measurements of fat thickness and subject satisfaction rates. As with the primary efficacy variable the assessment at Visit 8 (12-week follow up) will be primary. The analysis and summaries for caliper measurements will include a pairwise treatment group comparison as well as repeated measure ANOVA analysis. Statistical significance with respect to both the treatment and control group comparisons as well as repeated measures of the treatment group will be declared if the two-sided p-value is <0.05 . For each treatment group and timepoint of the caliper measurements a statistical summary will be completed. The summary will include sample size mean, median, standard deviation, minimum, and maximum. The statistical significance of the mean change from baseline to follow-up for each group as well between the treatment and control will be determined using a paired t-test. Subject satisfaction will be analyzed with standard descriptive statistics which include total number of responses in each category as well as the percentage of responses for each category. Clinical success of subject satisfaction surveys will be declared if at least 80% of subjects respond they are satisfied.

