2.16 Randomization

One flank will receive treatment with the TempSure® Firm handpiece and the other will not receive treatment to serve as a control. Randomization will occur using a validated method determined by the Investigator, such as flipping a coin or an electronic system such as Virtual Coin Toss (www.virtualcointoss.com).

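### Daily massage is prescribed for the treated flank but not the control, so the caliper comparison estimates device plus massage, not the device alone

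*Combined protocol and SAP*

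**What the plan says.** Section 2.4 (Screening) lists the post-treatment instructions reviewed with every subject. One of them reads: "Gently massage the treated area daily for 5 minutes for the duration of your involvement in the study".

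The comparator is the subject's other flank. Section 2.1 says "The other flank will be left untreated to serve a control". Section 2.16 randomizes one flank to the handpiece "and the other will not receive treatment to serve as a control".

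The caliper contrast between flanks is a secondary objective in section 1.1 and the second of four criteria in section 2.15.1 that must all be met for success: "Caliper measurements show statistically significant improvement on treatment area versus control". Section 2.15.5 states that the significance of the mean change "between the treatment and control will be determined using a paired t-test", at a two-sided p-value below 0.05. Section 2.2 describes the trial as a "multi-center clinical study to collect efficacy data on the TempSure® Firm".

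The schedule in section 2.12 and the evaluation methods in section 2.13 contain no record of massage. The analysis in section 2.15.5 does not mention it.

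**The concern.** A within-subject, split-body design is strong because both flanks share the same person, weight, diet and time. Any difference between them can then be credited to whatever was done to one flank and not the other. Here two things are done to one flank: radiofrequency treatment, and five minutes of massage every day until the end of the study. As prescribed, they always occur together on the treated side and are both absent from the control side. No analysis of the planned data can separate them.

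Criterion 2 is the only one of the four that uses the control flank. The photographic criterion compares before with after, satisfaction has no comparator, and the side-effect criterion is a physician's judgement. So the one place where the design could support attribution to the device is where the second intervention enters. The plan limits other influences: section 2.3 bars other procedures on the treatment area, and section 2.4 asks for constant weight and exercise. Massage is the exception. At stake is whether a positive caliper result can be reported as efficacy of the TempSure Firm itself.

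**Working it through.** **1. The plan's caliper sample size.** Section 2.15.2 gives changes of 7.0 mm (treated) and 0.7 mm (control), a standard deviation (SD) of 5.8 mm, significance level 0.05 and power 95%, and concludes that "it was determined that 14 subjects would be needed to have a successful secondary outcome measure".

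- Planned difference: 7.0 − 0.7 = 6.3 mm.
- Paired t-test, two-sided 0.05, with 5.8 mm taken as the SD of the paired difference: the solution is n = 13.1. Power is 94.8% at n = 13 and 96.3% at n = 14.

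The stated 14 is reproduced, so the plan in effect uses 5.8 mm as the SD of the between-flank difference.

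**2. How much massage is prescribed.** Inputs: 5 minutes daily (section 2.4), which is 35 minutes a week; up to 5 treatments 1 to 2 weeks apart (sections 2.7 and 2.12); last visit 12 ± 1 weeks after the final treatment (section 2.12). With k treatments, the weeks from first treatment to last visit are (k − 1) × (1 to 2) + (11 to 13).

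| Treatments | Weeks | Minutes (weeks × 35) | Hours |
|---|---|---|---|
| 1 | 11 to 13 | 385 to 455 | 6.4 to 7.6 |
| 5 | 15 to 21 | 525 to 735 | 8.75 to 12.25 |

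These are prescribed totals under full adherence. Actual massage is not recorded.

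**3. How small a difference meets criterion 2.** The smallest observed difference that reaches two-sided p < 0.05 is t(0.975, n − 1) × SD / √n.

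- n = 68 (planned enrollment): 1.996 × 5.8 / √68 = 1.40 mm, which is 22% of 6.3 mm.
- n = 43 (the overall requirement in section 2.15.2): 2.018 × 5.8 / √43 = 1.78 mm, which is 28% of 6.3 mm.

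Section 2.15.2 describes 5.8 mm as the largest SD of any single measurement, so the SD of the difference is uncertain. I take 4.1 to 8.2 mm as an assumed range (5.8/√2 to 5.8 × √2):

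| SD of difference (mm) | Threshold, n = 68 (mm) | Threshold, n = 43 (mm) |
|---|---|---|
| 4.1 | 0.99 | 1.26 |
| 5.8 | 1.40 | 1.78 |
| 8.2 | 1.99 | 2.52 |

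These are significance thresholds for a difference from any cause. They do not estimate a massage effect.

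**4. Illustration, by assumption only.** Suppose the device did nothing and massage alone reduced the treated flank by 1, 2 or 3 mm. The chance that criterion 2 would be met is:

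| Assumed massage effect | n = 68, SD 5.8 | n = 68, SD 8.2 | n = 43, SD 5.8 | n = 43, SD 8.2 |
|---|---|---|---|---|
| 1 mm | 29% | 17% | 20% | 12% |
| 2 mm | 80% | 51% | 60% | 35% |
| 3 mm | 99% | 84% | 91% | 65% |

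The documents support none of these effects, and zero is also possible. The table shows only that the test has no protection against a modest one.

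**The case against.** The strongest reply is that aftercare belongs to the regimen. The massage line sits beside advice on moisturizer and sun protection, and comparing a treatment together with its aftercare against no treatment is a legitimate pragmatic contrast. The caliper objective and criterion 2 speak of the treated area against control and never say device alone. This stands in part: the comparison is valid for the regimen. But the plan nowhere defines the intervention as device plus massage. Section 1.1 (Name and Intended Use) and section 2.2 tie the study to the device, which section 4.0 says is not cleared for lipolysis.

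Second, nothing in the documents shows that gentle massage changes skinfold thickness, and the only mechanism described in section 3.3 is heating. This stands. The size of any bias is unknown and may be nil. The design, however, cannot show that it is nil.

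Third, one-sided massage is inferred from silence about the other flank. The subject instruction sheet (Attachment IV), the Clinical Reference Guide (Attachment II) and the case report forms are not among the documents reviewed, and they might address the other flank or record compliance. That is a fair limit. The protocol text nevertheless names the treated area and defines the other flank as untreated.

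Fourth, the caliper result is secondary, and a massage-driven result could not by itself make the study a success because all four criteria are needed. This is true, but criterion 2 is still required and is the only controlled comparison among the four.

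**Conclusion.** The concern holds. As written, the caliper comparison estimates TempSure Firm plus prescribed daily massage versus no treatment. It cannot support a device-only conclusion.

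No corrected sample size or bias figure follows, because the documents give no massage effect. What can be sized is the exposure (8.75 to 12.25 hours with five treatments) and the low bar: about 1.40 mm with 68 subjects or 1.78 mm with 43, if 5.8 mm is the SD of the paired difference, and 0.99 to 2.52 mm across the assumed SD range and both sample sizes.

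The conclusion rests on reading the massage instruction as applying to the treated flank alone, which is what the protocol text says. What needs limiting is the claim; the test itself is valid for the regimen. The change should be made because it is cheap and settles what the trial can conclude.

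**What to change.** **Preferred, for subjects not yet started:** change the line in section 2.4 so that the same daily massage instruction covers both flanks, and describe the control accordingly in sections 2.1 and 2.16. The caliper contrast then isolates the device given equal aftercare. Record which instruction version each subject received and show the caliper result by version. The cost is a formal amendment with written IRB approval (section 21.0) and revised subject instructions. If some subjects have already started, there will be two instruction cohorts to report, and the later one may be small.

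**Otherwise:** word the caliper objective in section 1.1, criterion 2 in section 2.15.1 and the study report as TempSure Firm plus prescribed daily massage versus no treatment, and make no device-only claim. This costs a few lines and no extra data. The report wording can be used at any stage.

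For the photographic endpoint only the wording change helps. It compares images before and after treatment, so massaging both flanks would leave the massage in the later images.

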2.5 Informed Consent Process and Enrollment

Subjects will be asked to review the pre and post treatment instructions prior to signing the informed consent form and their involvement in the study. Subjects who sign the informed consent will be screened to confirm eligibility and, if eligible, will be assigned a subject identification number. Subjects will be de-identified through their subject identification number, which will be stored in a secure location. Subject identification numbers will be generated chronologically and assigned only to subjects who have met all the study selection criteria and have signed the informed consent form. The informed consent will be obtained prior to a subject's involvement in any study related procedures. A subject will be considered enrolled in the study once they have signed the informed consent form.

2.6 Pre-Treatment Procedures

If the subject is of childbearing potential (i.e. females not post-menopausal or not surgically sterile), they will be asked if they are pregnant, the date of their last menstrual cycle, and perform a urine pregnancy test. A urine pregnancy test will be performed on all women of childbearing potential prior to each treatment. A urine pregnancy test may also be conducted at the Investigator's discretion at any time during the study. If a urine pregnancy test is conducted, then a negative result must be obtained within 24 hours prior to the treatment.

Urine Pregnancy Test Procedure:

- A urine sample is tested mid-stream or by cup sample with an indicator stick.
- Negative results are indicated on the indicator stick.

- The area to be treated will be identified and may be marked with a surgical marker.
- Caliper measurements of both flanks will be taken prior to the first treatment and prior to treatment 4 and may be taken prior to other treatment visits as well.
- Photographs will be taken prior to the first treatment and prior to treatment 4 and may be taken prior to other treatment visits as well.
- The treatment area and the neutral pad area may be cleansed with water and soap and/or an alcohol wipe.
- The neutral pad will be placed on the back in an area determined by the Investigator to maintain standard energy settings and to require less power from the device during the treatment.

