2.9 Follow Up

- Subjects will receive a phone call 1 week (1-10 days) after each treatment to record side effects.
- The study subjects are required to return to investigator site for a follow up evaluation at 6 weeks and 12 weeks post last treatment.
- Photographs and caliper measurements of both flanks will be taken at all follow up visits.
- Subject's weight will be recorded at all follow up visits.
- Subject questionnaires will be performed at all follow up visits.
- Adverse events will be documented at all follow up visits.
- Some subjects may have an incomplete response or no response by the end of the study. After the subject has completed their participation in the study, a treatment on the untreated flank using the TempSure® Firm may be performed upon the subject's request at no cost.

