2.13 Evaluation Methods

Photographs:

Photographs will be taken prior to treatment 1, prior to treatment 4 (post treatment 3), and at all follow-up visits and may be taken at each treatment and will be used to assess safety and efficacy of treatment.

Blinded Evaluation:

Three blinded independent reviewers will perform a photographic evaluation in which they will be asked to identify pre-treatment images when compared to post treatment images. The reviewers will be Board Certified Dermatologists and be chosen based on availability and have relevant clinical experience. They will attend a training session prior to grading.

Caliper:

Caliper measurements on both flanks will be taken prior to treatment 1, prior to treatment 4 (post treatment 3), and at all follow-up visits and may be taken at each treatment.

Caliper Procedure:

The caliper device is a hand-held instrument like a compass, that is used to measure the distance between two opposite sides. The clinician will measure the flank by using a diagonal fold directly above the iliac crest. The patient's skinfold will be pinched approximately 1 cm from the measurement spot and the caliper will be placed on the skinfold. The caliper provides a measurement (millimeters) of the thickness of skin and fatty tissue. Three readings should be taken and an average of all three sites should be calculated and documented.

Treatment Discomfort/Pain Evaluation:

Subjects will be asked to report the general level of treatment discomfort on a scale of 0 (none) to 10 (maximum intolerable pain) using the universal pain assessment tool (Appendix B)

Subject Questionnaire:

The subject will be asked their level of satisfaction using a 6-point Likert scale that ranges from "extremely satisfied" to "extremely unsatisfied."

Subject Satisfaction	
Rating	Description
6	Extremely Satisfied
5	Satisfied
4	Slightly Satisfied
3	Slightly Unsatisfied
2	Dissatisfied
1	Extremely Unsatisfied

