2.14 Adverse Event Recording

All data captured must be supported by the Investigator's timely assessment and documentation of the adverse event in the case report forms or source documents. All documented adverse events will be reviewed by the Sponsor or designee to determine whether the adverse event meets regulatory reporting requirements and to ensure timely adverse event reporting to meet local and global regulatory requirements.

Adverse Events Pertaining to the TempSure Device:

Mild discomfort during treatment may be experienced by the subject. Typically, the discomfort is temporary and localized within the treatment area. Mild edema (swelling) and erythema (redness) may occur. Initial studies indicate that these side effects typically resolve within 2 to 24 hours.

Other anticipated side effects may include; pain, skin burns, bleeding, scarring, crusting, bruising, infection, itching,

prolonged edema (swelling) and erythema (redness), hardness, and nodules. Loss of hair pigment may also occur within and adjacent to the treatment area.

Adverse Events Pertaining to Gel:

The gel is a water-based gel that may be placed on the skin during the TempSure® Firm treatment. No known adverse events are documented. However, an allergic reaction is always possible when placing a topical gel onto the skin. Allergic reaction may include a mild reaction such as skin redness, irritation, or hives.

Adverse Events Pertaining to Neutral Pad:

Mild heat or hot spots may be felt during treatment by the subject. If the subject reports heat at the pad site, evaluate the site, check for epidermal injury. Skins burns may occur if subject does not report if the pad becomes too hot.

Adverse Events Pertaining to the Surgical Marker:

Using surgical marker has minimal risks and may produce effects on the body such as redness or a rash. Markings may remain visible for a few days or may be removed with alcohol.

Other Cautions:

Incomplete response or no response may occur since some subjects may not respond to treatment. After the subject has completed their participation in the study, a treatment on the untreated flank using the TempSure® Firm may be performed upon the subject's request at no cost.

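### Section 2.6 lists optional skin marking before the baseline photographs, so a site following that order could leave marks on the pre-treatment images alone and cue the blinded reviewers

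*Combined protocol and SAP*

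**What the plan says.** All references are to the combined protocol and SAP.

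- **Section 2.6, in listed order.** The marking bullet reads "The area to be treated will be identified and may be marked with a surgical marker". Caliper measurement is next, and then "Photographs will be taken prior to the first treatment and prior to treatment 4". After the photographs comes "The treatment area and the neutral pad area may be cleansed with water and soap and/or an alcohol wipe". Marking and cleansing are both optional.
- **Section 2.14** on the surgical marker: "Markings may remain visible for a few days or may be removed with alcohol".
- **Section 2.9** for the 6- and 12-week visits: "Photographs and caliper measurements of both flanks will be taken at all follow up visits". No marking step is listed there.
- **Section 2.13** gives the reviewers' task: "they will be asked to identify pre-treatment images when compared to post treatment images".
- **Section 2.15.5** makes the comparison of baseline with the 12-week visit primary, with 80% correct identification as the success threshold. It adds: "Baseline is defined as the last assessment prior to the first treatment".
- **Section 13.0** requires camera settings to be reproduced at each visit. It does not mention skin marks or any check of the images before they are graded.

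**The concern.** The reviewers' whole task is to tell which of two images came first. If ink appears on some baseline images and on no 12-week image, it answers that question without any change in fat. Correct identification in those pairs would then say nothing about the device.

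Having three reviewers does not help, because all of them see the same images and the same cue. The untreated flank has no stated role in the photographic success criterion (sections 2.15.1 and 2.15.5), so that analysis would not reveal the artefact. Section 3.2 relies on blinded evaluators to limit bias, and a visible mark would weaken that protection.

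**Working it through.** **Step 1: can a mark appear on one image of the pair only?** Set the sections side by side.

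- Before treatment 1, the 2.6 order is mark (optional), calipers, photographs, cleansing (optional). Followed as listed, any mark made is on the skin when the photograph is taken.
- Marks last a few days unless removed (2.14). The 12-week visit falls 12 weeks, plus or minus 1 week, after the last treatment (2.12), so ink from a treatment visit would be gone.
- No marking is listed at follow-up (2.9).
- Nothing in the document says that photographs precede marking, that marks are removed before imaging, or that marked images are screened.

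A mark in the scored pair would therefore be on the baseline image.

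**Step 2: the plan's own figure and the chance rate beneath it.** Section 2.15.2 assumes 50% correct (SD 50%) with no effect and 80% (SD 20%) as the objective, with two-sided alpha 0.05 and power 95%. It arrives at 43.

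n = (0.50² + 0.20²)(1.960 + 1.645)² / 0.30² = 0.29 × 12.995 / 0.09 = 41.87, or 42 by the normal approximation. With the t distribution on 2n − 2 degrees of freedom, power first reaches 95% at n = 43 (0.9506).

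The 43 is thus reproduced, as the size of each group in a two-sample formula. It rests on a 50% rate under no effect, and that rate assumes no cue in the images.

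**Step 3: the no-effect rate when some baseline images are marked.** Let m be the share of pairs whose baseline image carries a mark that the reviewer recognises. The documents do not give m, so the range 0 to 1 is an assumption. Marked pairs are identified with certainty and the rest at 50%:

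expected rate = m + (1 − m) × 0.5 = 0.5 + 0.5m.

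This equals 0.80 at m = 0.30 / 0.50 = 0.60.

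The table adds the binomial chance that one reviewer reaches 80% correct with no device effect. That takes at least 55 of 68 pairs (0.8 × 68 = 54.4) or 35 of 43 (0.8 × 43 = 34.4).

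| m | Expected correct | Chance, 68 pairs | Chance, 43 pairs |
|---|---|---|---|
| 0 | 50% | <0.0001 | <0.0001 |
| 0.2 | 60% | 0.0002 | 0.002 |
| 0.4 | 70% | 0.030 | 0.067 |
| 0.6 | 80% | 0.50 | 0.50 |
| 0.8 | 90% | 0.993 | 0.976 |

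These are upper limits for the rule in 2.15.5. Two of three reviewers is 67%, short of the required 80% of reviewers, so all three must reach the threshold.

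**Step 4: if the device has a modest effect.** With true identification rate p in unmarked pairs, the expected rate is p + (1 − p)m, which reaches 0.80 at m = (0.80 − p)/(1 − p). For p = 0.60, m = 0.20/0.40 = 0.50. For p = 0.70, m = 0.10/0.30 = 0.33.

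**The case against.** The strongest reply is that 2.6 is an inventory and not a sequence. Its bullets are unnumbered and nothing calls them an order of work. Read strictly in order, the list partly defeats itself: an alcohol wipe after marking could erase the marks before the treatment they are meant to guide. Marking is also optional. The schedule in 2.12 places photographs at the screening visit too, which need not fall on the day of treatment 1, so photographs and marking may not coincide. The Clinical Reference Guide, the sponsor's procedures and the site training are not in the file and may cover photography.

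Most of this stands, and it limits the point to a risk that the text leaves open. It does not remove the risk. With up to 6 centers, a site can follow the list as written and comply fully. Where photographs are taken both at screening and before treatment 1, the baseline definition in 2.15.5 selects the later one, which is closer to any marking.

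Two stronger readings are tempting, and the documents support neither.

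- **Shaving as a second cue.** A reader might infer this from the instruction "Shave any dense hair on the area to be treated" in 2.4. It covers dense hair only. Nothing says that hair will differ at week 12 or that reviewers know shaved skin means pre-treatment. With same-day screening and treatment, the baseline image could even be unshaved.
- **Identification driven to 100%.** A reader might infer that marks make success certain whatever the device does. That needs m near 1 and every mark recognised. Study success also requires the caliper, satisfaction and side-effect criteria in 2.15.1.

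**Conclusion.** The concern holds as an uncontrolled risk to the primary endpoint. The documents do not show that unblinding will occur. A site working in the listed order could put ink on the baseline image alone, and the 50% chance rate assumed in 2.15.2 would then no longer apply to those pairs.

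The size depends on m, which is unknown. With no device effect, marks alone would almost never carry a reviewer to 80% at m of 0.2 or less, would seldom do so at 0.4, and would do so about half the time at 0.6. So the bias is small if marking is rare and serious only if it is common.

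These figures assume that every mark is recognised, that unmarked pairs are at 50%, and that pairs are independent. If some marks go unnoticed, the effect is smaller for the same number of marked images.

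**What to change.** In 2.6 and 13.0, state that study photographs are taken before any skin marking, or after marks have been fully removed.

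For photographs already taken, have someone not involved in grading check the baseline and 12-week images for visible marks before release to the reviewers, and record which pairs are marked. Report the identification rate with and without the marked pairs as a sensitivity analysis. Doing the check before grading keeps the list of marked pairs independent of the reviewers' answers, and it gives the value of m that the plan lacks.

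The cost is two lines of protocol wording, one pass through the images and one extra line in the results. Treatment and sample size do not change. Photographing before marking asks nothing more of subjects.
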